As a proof-of-concept, we have also directly examined thalamo-prefrontal functional connectivity before and after tDCS intervention. To determine whether tDCS can directly affect thalamocortical connectivity, subjects were randomized to either active tDCS (n=6) or sham tDCS (n=5). Rest fMRI data was collected pre- and post-intervention. Intervention consisted of either cognitive training + active-tDCS or cognitive training + sham-tDCS twice a day (two 13 minute sessions per day, each 2mA / 25cm² = 0.08 current density; anode on left dorsolateral prefrontal cortex F3, cathode on right dorsolateral prefrontal cortex F4) for five consecutive days. Preliminary analyses examining FC between left thalamus and left dorsolateral prefrontal cortex showed that subjects assigned to active-tDCS (n=6) showed a within-group increase in FC ($t=2.05$, $p=0.096$) while subjects assigned to sham-tDCS (n=5) did not show a significant within-group FC change ($t=1.103$, $p=0.332$). Group x Time effects was eta-square $\eta^2=0.353$. These pilot data suggest tDCS can improve thalamocortical connectivity.

PROTOCOL TITLE: Increased thalamocortical connectivity in tDCS-potentiated generalization of cognitive training

VERSION DATE: January 26, 2023

2.3 Existing Literature:

Task-dependent Nature of tDCS-enhanced Neuronal Plasticity. A growing consensus suggests tDCS acts as a modulator of ongoing synaptic activity to facilitate task-relevant plasticity. For example, anodal tDCS enhanced the induction of long-term potentiation (LTP) between concurrently active neurons in slice, but had no effect on inactive neurons (Kronberg, Bridi, Abel, Bikson, & Parra, n.d.). In living mice, a combination of training with stimulation enhanced both cortical LTP and motor learning in contrast to stimulation alone (Fritsch et al., 2010). This underscores the need for ongoing cognitive activity to realize the potential of tDCS.

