
Analyses to test SA2, that generalization and durability are driven by right tDCS more than left tDCS or sham (H2.1), longer treatment length (H2.2) and higher modeled dosage (H2.3) will be conducted both between and within groups (for both Studies 1 and 2). The first step will establish the existence of between-group training effects using repeated-measures ANOVA’s on the key performance outcome variables (d' scores for the word and picture N-backs, d'-context for the DPX, and the composite score for MCCB). We will also evaluate differences in self-rated engagement and experimenter-rated Work Behavior Inventory (Bryson et al., 1997), sleep patterns, age, baseline IQ, and these will be used as covariates of non-interest as appropriate.

PROTOCOL TITLE: Increased thalamocortical connectivity in tDCS-potentiated generalization of cognitive

training

VERSION DATE: January 26, 2023

To examine SA3, the relationship between thalamocortical FC change and generalization and durability, we will examine the nonparametric relationships between changes in thalamocortical connectivity and improvements on the trained task (word N-back d'), proximal transfer (picture N-back d'), and more distal generalization (DPX d', MCCB composite score) and durability (H3.1 and H3.2 respectively). If analysis of covariates suggest that there are important sources of within-group variance in learning (e.g. age, baseline IQ, etc.), then hierarchical regressions will be used on Fisher's transformed z-scores of thalamocortical connectivity. In addition, to determine whether thalamocortical FC changes predict stability in learning and generalization, task performance at 24 weeks will also be subjected to hierarchical regressions. The regression model will enter covariates on step 1, and thalamocortical connectivity on step 2. The statistician will be blind to condition until analyses are completed.

In all cases, these relationships will be tested separately for Cohort 1 and Cohort 2, as changes associated with improvement are likely to be different for groups with different mean levels of ability. Follow-up analyses will determine the extent to which these observed differences suggest actual differences between these populations. However, the current study is not designed to directly compare the populations.

15.2 Power Analysis:

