75 completers in cohort 1 and cohort 2 will provide power of .80 to detect effects as small as $\eta^2=.03$ for key confirmatory analyses (tested at $\alpha = .05$) and $\eta^2=.05$ for other analyses (tested at $\alpha=.005$), with nearly as strong power for the analysis of the 24 week follow-up. The more conservative approach of intent-to-treat analysis ($n=90$) will also be conducted for Cohort 2, for which the study will be sensitive to $\eta^2=.027$ (tested at $\alpha = .05$) and $\eta^2=.042$ (tested at $\alpha = .005$). These effect sizes are much smaller than the group x time effect for generalization as measured by the MCCB in our pilot tDCS data ($\eta^2=.08$), suggesting the proposed study is well-powered. While power analyses for neuroimaging studies are challenging due to the interactions of voxelwise-thresholds, brain-wise error correction and spatial smoothness, the proposed studies will be well-powered to detect group x time voxel differences as small as $\eta^2=0.07$ (tested at $\alpha = .001$), and in any case the samples are twice the size of our previous, successfully replicated, neuroimaging studies of brain change following cognitive remediation. Within-group responder analyses conducted for completers ($n=25$ per cell) will have power of .80 to detect correlations $r \geq .34$, a lower magnitude than we already observed ($r=.55$).

15.3 Statistical Analysis:

See section 16.1

15.4 Data Integrity:

The investigator is responsible for ensuring the accuracy, completeness, legibility, and timeliness of the data reported. To enhance scientific rigor, avoid bias and enhance reproducibility, our triple-blind randomized design will use a stratified permuted block randomization procedure (Matts & Lachin, 1988) to roughly equate age and baseline WM performance across groups with a block size of 6. Neither participants nor experimenters will know group assignment. TDCS software programming will allow staff to randomly select one of the three hemisphere conditions (right, left, sham) corresponding to eight letters (six to be distributed evenly among three conditions for HCs, two to be distributed evenly among two conditions for SZs) encoded to preserve the blind. Randomization will be facilitated and the blinding code will be maintained by the study statistician.

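### As written in 15.1, the SA3 tests name no arm term, so pooling arms can produce an FC-performance association from arm means alone, with a false-positive rate of up to about 30% instead of 5%

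*Combined protocol and SAP*

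**What the plan says.** For SA3, section 15.1 begins with rank-type association: "we will examine the nonparametric relationships between changes in thalamocortical connectivity and improvements on the trained task (word N-back d"; the same is planned for the picture N-back, the DPX and the MCCB composite. Regression on FC change follows only on a condition: "If analysis of covariates suggest that there are important sources of within-group variance in learning (e.g. age, baseline IQ, etc". For durability there is no condition: "task performance at 24 weeks will also be subjected to hierarchical regressions". In both cases the order of entry is: "The regression model will enter covariates on step 1, and thalamocortical connectivity on step 2".

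The covariates named in 15.1 are self-rated engagement, the Work Behavior Inventory and "sleep patterns, age, baseline IQ, and these will be used as covariates of non-interest as appropriate". Treatment arm is not among them. The one split that is stated is by cohort: "In all cases, these relationships will be tested separately for Cohort 1 and Cohort 2".

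Section 15.2 adds a different analysis, "Within-group responder analyses conducted for completers", at 25 per cell. It claims power .80 for correlations of .34 or more and compares that with the pilot r=.55, which section 2.2 reports inside the experimental arm of a training study.

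**The concern.** H3.1 and H3.2 are the mechanistic claims: section 3.1 says that greater FC drives generalization and durability. They are of interest only if they add to SA1 and SA2, which ask whether stimulation changes FC and performance.

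Within a cohort, participants in different arms may differ in mean FC change and in mean performance change. A correlation pooled over arms mixes that between-arm pattern with the person-level link inside arms. If the arm means line up, the pooled test can be positive when people whose FC rose more than that of others in their own arm gained no more than those others. A positive SA3 could then restate SA1 and SA2 and be read as separate evidence that FC carries the benefit.

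**Working it through.** **Inputs.** 75 completers per cohort (15.2). Three arms in Cohort 1, so 75/3 = 25 each; two arms in Cohort 2, so about 37 each (5.1, 5.2). FC effect: section 2.2 states "Group x Time effects was eta-square" .353, from 6 active and 5 sham subjects. MCCB effect: eta-squared .08 (15.2). Plan's benchmark for detectable FC differences: .07 (15.2). The values .15 for FC and .03 to .05 for performance are assumptions that fill in the range. Eta-squared is read as the share of change-score variance lying between arms. Alpha is .05; 15.2 does not give sidedness.

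**1. The plan's own figure.** Power = Φ(atanh(r)·√(n−3) − z). With r=.34 and n=25: atanh(.34) = .354, √22 = 4.690, product 1.661.
- Two-sided: Φ(1.661 − 1.960) = 0.38.
- One-sided: Φ(1.661 − 1.645) = 0.51.
- Detectable r at power .80: tanh((1.960 + .842)/4.690) = .535 two-sided; tanh((1.645 + .842)/4.690) = .485 one-sided.
- r=.34 needs about 66 per cell two-sided, or 53 one-sided.

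The stated .80 is not reproduced. At 37 per arm (Cohort 2) power is 0.54 two-sided and 0.66 one-sided.

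**2. Correlation induced by pooling.** With zero association inside every arm, pooled r = √(η²_FC × η²_perf) × a, where a is the correlation between the two patterns of arm means (a = 1 for two arms moving the same way). The two-sided rejection rate is Φ(d − 1.960) + Φ(−d − 1.960), with d = atanh(r)·√(n−3) and √72 = 8.485 at n=75.

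| η² FC / performance | Induced r | d | Rejection rate |
|---|---|---|---|
| .353 / .08 | .168 | 1.44 | 0.30 |
| .15 / .08 | .110 | 0.93 | 0.15 |
| .07 / .08 | .075 | 0.64 | 0.10 |
| .07 / .05 | .059 | 0.50 | 0.08 |
| .07 / .03 | .046 | 0.39 | 0.07 |

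**3. Three arms.** H1.1 concerns FC on the stimulated side, and H2.1 places right above left and sham. In the order right, left, sham:
- FC raised in both active arms (1,1,0), performance in right only (1,0,0): a = 1/2, so r = .168/2 = .084.
- FC raised by left only (0,1,0), performance by right only (1,0,0): a = −1/2, so r = −.084.

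**4. Simulation.** 10,000 trials per row, no link inside any arm, η² .353/.08, two-sided .05.

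| Setting | Mean r | Pooled rank test | Arm-adjusted |
|---|---|---|---|
| 2 arms × 37 | .17 | 0.31 | 0.048 |
| 3 × 25, both active arms raised on both measures | .17 | 0.31 | 0.048 |
| 3 × 25, right only raised on both measures | .17 | 0.30 | 0.047 |
| 3 × 25, FC both active, performance right only | .09 | 0.11 | 0.046 |
| 3 × 25, FC left only, performance right only | −.085 | 0.11 (nearly all negative) | 0.051 |

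A test inside a single arm also stays at about 0.05.

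**5. Power with arm in the model.** For a common within-arm r=.34 with 70 in place of n−3: √70 × .354 = 2.96, and Φ(2.96 − 1.96) = 0.84. Simulation gave 0.85, against 0.85 to 0.86 pooled without arm.

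**The case against.** The best defence is that SA3 is meant to be run inside each arm. Section 15.2 powers correlations per cell, 25 is 75 divided by three arms, and the comparison value of .55 was a within-arm correlation. The regression in 15.1 is also triggered by variance within groups. On that reading the artefact disappears. The reading is possible, but 15.1 does not state it. There the only separation is by cohort, and the same paragraphs use the word groups for the cohorts. Nor would it rescue the plan: 25 per cell fits only the three-arm cohort, and power for r=.34 is about half of what is claimed.

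Four further objections stand and limit the point.
- The covariate list is open-ended, so arm is left unspecified rather than excluded.
- The .353 comes from 11 subjects after five days of treatment, and the active group's own change had p=.096. The plan's own benchmark is .07.
- A reader might infer that H1.1 and H2.1 together predict gains on both measures in every active arm. They do not. H2.1 sets right against left and sham, and Cohort 2 has only left and sham. The Cohort 2 rate therefore rests on carrying over the pilot .08, not on H2.1.
- H3 does not claim that the link differs between arms, so an arm-by-FC term is not needed to test it.

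**Conclusion.** The gap is real: no arm term is named for the SA3 rank test or for either regression, and any version pooled over arms can pick up arm-mean covariation. With no within-arm link and about 75 completers, the false-positive rate is up to about 30% at the pilot effects, about 15% at .15/.08 and 7 to 10% at the .07 benchmark, against 5% with arm in the model. In Cohort 1 it depends on the arm pattern: about 30% when aligned, about 11% when partly aligned, and a negative association when FC and performance respond to opposite sides.

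A reader might infer that success on SA1 and SA2 makes a positive SA3 likely by itself. The figures do not support that. Even among simulated trials in which both arm effects reach p<.05, the aligned case gives roughly 40% at the pilot effects and 12 to 14% at .07/.05. The induced r, at most about .17, is also far below the pilot .55.

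The rates assume normal change scores, two-sided .05 and eta-squared as defined above. The 24-week regression uses performance level rather than change, so its rate may differ. Section 4.1 expects a smaller Cohort 2, and remote participants have no MRI. With 50 analysed, the rate at the pilot effects falls to about 21%, and per-arm power falls too.

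**What to change.** In 15.1:
- Enter masked arm indicators at step 1 of every SA3 regression, including the 24-week one and whatever the covariate screen shows. Enter FC change at step 2, and name that common within-arm slope as the H3 test.
- For the rank test, use within-arm ranks or a partial rank correlation given arm.
- Report per-arm estimates and an arm-by-FC-change term as supportive. The interaction is needed only if a difference between arms in the link is to be claimed.

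In 15.2, restate the per-cell power: at n=25 the detectable correlation at power .80 is about .49 (one-sided) to .54 (two-sided). Give a separate figure for the two-arm cohort.

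The cost is wording plus 1 degree of freedom in Cohort 2 and 2 in Cohort 1. Power for a common within-arm r=.34 stays at about .84 with about 75 completers; a rank version will be slightly lower. Masked codes keep the blind, and 15.1 already plans arm contrasts for SA1 before unblinding. Because 15.4 assigns six letters to three arms in Cohort 1, the analyst needs the letters collapsed to three masked labels; six separate letters would cost 5 degrees of freedom.

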4.0 Study Intervention(s)/Investigational Agent(s)

4.1 Description:

This study will include 2 cohorts of participants (healthy controls and patients with schizophrenia) in order to evaluate how anodal tDCS with concurrent WM focused training affect thalamocortical connectivity, how this may differ from right vs. left (hemisphere) vs. sham stimulation, how the number of sessions (length of treatment) and modeled dose impacts proximal transfer and generalization, how they are affected by other psychologically and biologically relevant variables, and the durability of these cognitive changes after training.

PROTOCOL TITLE: Increased thalamocortical connectivity in tDCS-potentiated generalization of cognitive training

VERSION DATE: January 26, 2023

For the proposed project, participants in cohorts 1 and 2 will undergo a similar protocol, consisting of WM training concurrent with tDCS. This training will consist of a target of 30 sessions of 45 minutes each in 11-12 weeks (target average density of 3 sessions/week), with a minimum of 24 sessions (and a minimum average density of 2/week). Due to limited reach to the schizophrenia population during the global pandemic, cohort 2 is expected to be a smaller sample size than originally anticipated. We will only be studying left hemisphere stimulation in cohort 2 subjects.

The tDCS will be performed with Neuroelectrics Starstim8 (Neuroelectrics Barcelona, Spain). This device has been approved for use in research without an investigational device exemption due to meeting criteria for non-significant risk. In addition, the device has built in safety mechanisms which allow for the immediate cessation of stimulation should the subject become uncomfortable or impedance levels too high.

The Starstim software supports the measurement of electrode impedance (Neuroelectrics, 2016). Before each training session, the impedance of the electrodes will be checked and verified to be ≤ 10 KOhm. During a training session, the impedance is measured every second and if found to be > 20 KOhm stimulation will be terminated for safety. The current and impedance will be recorded for every session (Ruffini, 2016) (implemented in Dec 2016, NIC v2.1).

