5.0 Procedures Involved

5.1 Study Design:

This is a triple-blind, randomized placebo-controlled clinical trial (with blinded subjects, experimenters and statisticians) with healthy controls (cohort 1) and schizophrenia patients (cohort 2). 90 HCs, after signing consent and determining eligibility will be enrolled and randomized to receive either (i) Active 2mA right (AF4

PROTOCOL TITLE: Increased thalamocortical connectivity in tDCS-potentiated generalization of cognitive training

VERSION DATE: January 26, 2023

anode-AF3 cathode) or (ii) Active 2 mA left (AF3 anode-AF4 cathode), or (iii) Sham 0 mA tDCS during concurrent WM focused training for a total of 12 weeks. 90 SZ patients, after signing consent and determining eligibility will be enrolled and randomized to receive either (i) Active 2 mA left (AF3 anode-AF4 cathode), or (ii) Sham 0 mA tDCS during concurrent WM focused training for a total of 12 weeks. For the active stimulation, current will ramp-up for 30 seconds, remain at 2mA for 20 min and then ramp-down for 30 seconds at the end of the stimulation session. For sham stimulation, the electrodes will be placed at the same positions as for active stimulation (AF3 and AF4), but current will be turned off immediately after the initial 30 second ramp-up period. Thus, participants will feel the initial itching sensation associated with tDCS but will receive no active current for the rest of the stimulation period. This method of sham stimulation has been shown to be reliable(Gandiga, Hummel, & Cohen, 2006). To test the effects of dosage, we have scheduled a midtest and MRI scan after 6 weeks of training (approximately 15 sessions), and a posttest and scan at the completion of the protocol after 12 weeks (approximately 30 sessions). The assessment battery will be completed again at follow-up 12 weeks after the final training session.

5.2 Study Procedures:

Pre-Screening for Cohort 1 (healthy controls): Study staff or weblinks will direct interested individuals to a HIPAA compliant online portal with a thorough description of the requirements of the study. At this time, interested individuals will answer relevant screening questions, including tDCS or MRI contraindications. Volunteers will also complete items from a neuropsychological vocabulary test to estimate crystalized IQ. If the HC volunteer fulfills inclusion and exclusion criteria, they will be invited to participate and scheduled for the pretest assessment.

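### Section 15.2 states Cohort 2 sensitivity for 75 completers and 90 randomised, a size that section 4.1 no longer expects and does not replace with a number

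*Combined protocol and SAP*

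**What the plan says.** Section 15.2 is the plan's only sample-size justification. It states that "75 completers in cohort 1 and cohort 2 will provide power of .80 to detect effects as small as" an eta-squared of .03 for key confirmatory analyses (alpha .05) and .05 for other analyses (alpha .005). It adds: "The more conservative approach of intent-to-treat analysis ($n=90$) will also be conducted for Cohort 2", with detectable values of .027 and .042 at the same two alphas. It then refers to "Within-group responder analyses conducted for completers ($n=25$ per cell", without naming a cohort. It judges the study to have good power by comparison with a pilot value of .08: "These effect sizes are much smaller than the group x time effect for generalization as measured by the MCCB in our pilot tDCS data".

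Section 4.1 says, because of the pandemic, that "cohort 2 is expected to be a smaller sample size than originally anticipated" and "We will only be studying left hemisphere stimulation in cohort 2 subjects". No reduced number is given. Section 5.1 nevertheless keeps the original figure: "90 SZ patients, after signing consent and determining eligibility will be enrolled and randomized to receive either (i) Active 2 mA left" or sham. Sections 10.1 and 23.1 also keep 90 patients, and the study summary keeps a total of 180. The two-arm allocation of Cohort 2 appears in 5.1, in 5.2, and in 15.4, where the blinding letters are described as "two to be distributed evenly among two conditions for SZs".

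**The concern.** Section 15.1 tests the two cohorts separately, so Cohort 1 cannot make up for a shortfall in Cohort 2. If Cohort 2 ends smaller, as 4.1 expects, a null result in patients would be read against a sensitivity stated for 75 completers or 90 randomised that the trial may not have. The statement in 15.2 and the expectation in 4.1 stand together in the current version, and nothing in 15.2 tells the reader that its Cohort 2 basis has moved.

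A second, lesser matter is that 15.2 does not say what kind of eta-squared it uses. The comparison with the pilot .08, on which the conclusion about power leans, has meaning only if both values are on the same scale.

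**Working it through.** **1. Cohort 2 size, section by section.** Study summary: 180 in total. Section 4.1: smaller than planned, no number. Sections 5.1, 10.1 and 23.1: 90. Section 15.2: 75 completers, and 90 for intent-to-treat. These cannot all describe the current expectation.

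**2. Cell sizes.** Three arms: 75/3 = 25 per cell, which matches Cohort 1. Two arms: 75/2 = 37.5, so 37 or 38 per cell; conversely 25 × 2 = 50 completers. If the per-cell sentence is meant to cover Cohort 2, it conflicts with 75 completers. If it describes Cohort 1 only, there is no conflict, but Cohort 2 has no stated cell size.

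**3. Reproducing the stated figures.** I read the 75 as per cohort. Section 15.2 gives no visits, visit correlation or test, so these are assumed: omnibus group × time F test, sphericity, g arms, m visits, correlation ρ.

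- f² = η²/(1 − η²); df1 = (g − 1)(m − 1); df2 = (N − g)(m − 1)
- planning scale: λ = f²·N·m/(1 − ρ); power from the noncentral F

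| Assumed setting | N=75, α .05 | N=75, α .005 | N=90, α .05 | N=90, α .005 |
|---|---|---|---|---|
| Stated in 15.2 | .03 | .05 | .027 | .042 |
| 2 arms, 2 visits, ρ .41 | .0307 | .0524 | .0256 | .0437 |
| 3 arms, 2 visits, ρ .5 | .0324 | .0532 | .0270 | .0442 |
| 3 arms, 3 visits, ρ .4 | .0318 | .0499 | .0265 | .0416 |

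The figures are approached but not matched exactly. The fits alone do not identify the number of arms; 75 with 25 per cell does point to three.

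**4. Two arms at smaller N.** Worked case, 2 visits, ρ .5, η² = .03, α .05: f² = .03/.97 = .0309. At N = 75, λ = .0309 × 75 × 2/.5 = 9.28, df 1 and 73, power .852. At N = 50, λ = 6.19, df 1 and 48, power .683. All three settings with two arms, α .05 (completer numbers below 75 are assumptions):

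| Completers | Power for .03: m=2 ρ .5 / m=3 ρ .4 / m=2 ρ .41 | Detectable η² at 80% power |
|---|---|---|
| 75 | .852 / .864 / .790 | .0262 / .0256 / .0307 |
| 60 | .764 / .773 / .694 | .0327 / .0319 / .0384 |
| 50 | .683 / .687 / .612 | .0393 / .0382 / .0460 |
| 40 | .582 / .580 / .514 | .0491 / .0477 / .0575 |
| 30 | .460 / .451 / .402 | .0656 / .0635 / .0765 |

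The smallest N with 80% power for .03 is 66, 64 and 77 in the three settings. At fixed N = 75, 2 visits and ρ .5, going from three arms to two lowers the detectable value from .0324 to .0262, so the arm change on its own does not cost power.

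**5. Scale of eta-squared.** On the partial scale λ = f²·df2. For the omnibus test at N = 75, α .05 and 2/3/4 visits, the detectable value is .0994/.0631/.0482 with two arms and .1225/.0789/.0610 with three; none is .03. Two-arm power for the pilot .08 at α .05:

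- if .08 is on the planning scale: 82-89% even at 30 completers
- if .08 is partial eta-squared, 2/3/4 visits: 70/90/97% at 75 completers and 33/47/59% at 30

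**The case against.** The best defence is that no loss has been demonstrated. Section 4.1 discloses the reduction openly, the completer numbers below 75 are assumed here, and in two of the three settings .03 is still reached with 64 to 66 completers. A modest shortfall might cost nothing against the stated figure. On the planning scale the pilot .08 would remain detectable even at 30. All of that stands, and it limits the claim to a stated basis that is out of date, with a consequence of unknown size. It does not remove the conflict, since 15.2 offers no other Cohort 2 number.

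Four stronger readings are tempting, and the documents do not support them:

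- *Cohort 2 is underpowered.* The reduced number is not given, so this cannot be shown.
- *Dropping to two arms cut the power.* At equal N it does the opposite.
- *The 25 per cell is a flat contradiction.* The sentence names no cohort and fits Cohort 1 exactly.
- *The eta-squared figures are miscalculated, or cannot be partial eta-squared.* The mismatch is shown only for the omnibus group × time test with 2 to 4 visits. A single-degree-of-freedom contrast on the partial scale (two arms, 4 visits) comes within 6-17% of the stated values, so the scale is unstated, not proven wrong.

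**Conclusion.** The point holds as an internal inconsistency in a stated power figure, not as an arithmetic error. Section 15.2 ties Cohort 2 sensitivity to 75 completers and 90 randomised, while 4.1 no longer expects the original size. The consequence depends on a number that the documents do not give. Under the three assumed two-arm settings, 80% power for .03 needs roughly 64 to 77 completers, so the margin below 75 ranges from none to 11. At the completion rate that 15.2 implies (75/90), 64 to 77 completers corresponds to about 77 to 93 randomised (64 × 90/75 = 76.8; 77 × 90/75 = 92.4).

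The unstated type of eta-squared is secondary. It is missing detail, and it leaves the comparison with the pilot .08 unsupported until both values are put on one scale; that comparison may well prove correct.

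**What to change.** - Restate 15.2 by cohort: three arms for Cohort 1, and two arms at the currently expected number for Cohort 2, giving completers, intent-to-treat n and per-cell n.
- Recompute the detectable effects at those numbers on a named eta-squared scale, and express the pilot .08 on the same scale. Keep the statements that the detectable effects lie far below the pilot value and that the study has good power only where the restated figures support them.
- Say which cohort the 25 per cell describes.
- Reconcile the Cohort 2 size across the study summary, 4.1, 5.1, 10.1, 15.2 and 23.1.

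This is a text change; no extra enrolment or visits are proposed. The only cost is that the stated Cohort 2 sensitivity may become less favourable.

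### The detectable eta-squared of .03 in section 15.2 is not on the scale the planned ANOVA will report, so setting it against the pilot .08 does not show that the study is well powered

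*Combined protocol and SAP*

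**What the plan says.** Section 15.2 of the combined protocol and SAP states: "75 completers in cohort 1 and cohort 2 will provide power of .80 to detect effects as small as" an eta-squared of .03 at alpha .05, and .05 at alpha .005. For an intent-to-treat analysis of 90 in Cohort 2 it gives .027 and .042. For imaging it claims sensitivity to "group x time voxel differences as small as $\eta^2=0.07$ (tested at $\alpha = .001". The benchmark is the pilot MCCB result: "These effect sizes are much smaller than the group x time effect for generalization as measured by the MCCB in our pilot tDCS data", given as .08. The adequacy claim for MCCB generalization rests on that comparison.

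Section 15.1 says that between-group training effects will be tested by repeated-measures ANOVA, with the MCCB composite among the outcomes. The schedules of events in 5.2 place the MCCB at baseline and weeks 6, 12 and 24. Section 15.2 does not say which eta-squared is meant, how many visits enter the test, or what within-person correlation was assumed. For the pilot .08 it also gives no sample size or number of arms.

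**The concern.** Eta-squared for a group x time effect can be scaled in more than one way. A repeated-measures ANOVA normally reports the partial form, in which the effect is set against the interaction error. Some power calculations set it against the variance between people at a single visit and bring in the within-person correlation separately. The same effect then has a much smaller eta-squared. If .03 is on the second scale and .08 on the first, placing them side by side makes the study look far more sensitive than it is.

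What is at stake is the reading of a null MCCB result in Cohort 1. A reader who trusts 15.2 would take it as strong evidence against an effect of the pilot's size, when power for that effect may have been well below .80.

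**Working it through.** **Inputs.** From 15.2: N = 75 completers, 25 per cell (hence three arms, k = 3), power .80, the five stated sensitivities and the pilot .08. From 10.1: 90 enrolled. From 2.2: the connectivity pilot, active n = 6 with t = 2.05, sham n = 5 with t = 1.103, and group x time eta-squared .353. Assumed because not stated: number of visits m, within-person correlation rho, and sphericity when m is above 2.

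**Formulas.** f² = eta²/(1 − eta²). The test is a noncentral F with df1 = (k − 1)(m − 1) and df2 = (N − k)(m − 1).
- Scaled to single-visit variance: lambda = f² × N × m/(1 − rho).
- Partial: lambda = f² × N × (m − 1), so partial eta² = lambda/(lambda + N(m − 1)).

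**Step 1. Reproduce the plan's figures.** Three arms, two visits, rho .5, single-visit scale:

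| N, alpha | lambda for .80 power | Reproduced | Stated |
|---|---|---|---|
| 75, .05 | 10.05 | .0324 | .03 |
| 75, .005 | 16.86 | .0532 | .05 |
| 90, .05 | 9.97 | .0270 | .027 |
| 90, .005 | 16.64 | .0442 | .042 |
| 75, .001 | 21.68 | .0674 | .07 |

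Four of the five agree after rounding. This is not the only setting that fits. Three arms, three visits and rho .39 give .0324, .0507, .0270, .0423 and .0626. Two arms, two visits and rho .41 give .0307, .0524, .0256, .0437 and .0676. All three settings use the single-visit scale.

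**Step 2. Detectable partial eta-squared, Cohort 1, N = 75, alpha .05.**
- Two visits: 10.05/(10.05 + 75) = .118
- Three visits: 12.33/(12.33 + 150) = .076
- Four visits: 14.03/(14.03 + 225) = .059

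At two visits the values are 16.86/91.86 = .18 for alpha .005 and 21.68/96.68 = .22 for alpha .001. Even with two arms and four visits the minimum is .047. No design tried (two or three arms, two to four visits) reaches .03 on the partial scale. The stated .03 is between .03/.118 = .25 and .03/.059 = .51 of the three-arm partial value.

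**Step 3. Which scale is the pilot .08 on?** The one pilot group x time figure that can be checked is in 2.2 ("Group x Time effects was eta-square" .353). In SD units the changes are 2.05/√6 = .837 and 1.103/√5 = .493. Take equal SDs; √(1/6 + 1/5) = .6055.
- Opposite directions: t = (.837 + .493)/.6055 = 2.197, partial eta² = t²/(t² + 9) = .349.
- Same direction: t = (.837 − .493)/.6055 = .567, partial eta² = .035.

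On the single-visit scale with two visits and rho .5, .353 would need t of about √(4 × 9 × .353/.647) = 4.4. So .353 looks like a partial value, provided the sham change ran opposite to the active change. Section 2.2 does not give the sham direction.

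**Step 4. Power for .08 in Cohort 1** (f² = .08/.92 = .0870), N = 75, alpha .05:

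| Reading of .08 | lambda | df | Power |
|---|---|---|---|
| Partial, two visits | 75 × .0870 = 6.52 | 2, 72 | .603 |
| Partial, three visits | 150 × .0870 = 13.04 | 4, 144 | .825 |
| Partial, four visits | 225 × .0870 = 19.57 | 6, 216 | .927 |
| Single-visit scale, two visits, rho .5 | 300 × .0870 = 26.09 | 2, 72 | .996 |

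For the pre-post partial reading, all 90 enrolled give .69, and 75 at alpha .005 give .27. At alpha .005 the three- and four-visit partial readings give .53 and .73.

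**The case against.** The strongest reply is that the documents never define the pilot .08, so no mismatch of scales is proven. The support from 2.2 comes from a connectivity measure in 11 people, not the MCCB, and needs the sham t to be reversed in sign. Two visits is also an inference: 15.1 describes group x time for imaging over three occasions, the MCCB is scheduled at four, and other settings fit the plan's figures about as well. With three visits the detectable .076 lies below .08. All of this stands.

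It rules out two stronger readings that a reader might draw. One is that Cohort 1 simply has .60 power for the pilot effect. The other is that on a common scale the comparison reverses. Both need .08 to be a pre-post partial value and the trial's test to be pre-post, and the documents state neither. The .60 also carries the pilot value unchanged to a three-arm omnibus test: the same partial .08 on a single degree of freedom gives about .71, and a two-arm .08 carried to three arms about .55. A pre-post partial .08 tested over three visits gives .49 to .63, depending on whether the mid-visit effect is halfway or already complete.

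The reply does not rescue .03 as a partial eta-squared. That result does not depend on the visits, the correlation or the pilot.

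**Conclusion.** Wrong as written, and should be fixed; confidence is moderate. The firm part is that .03 with 75 completers is not the quantity the ANOVA will report. The Cohort 1 partial sensitivity is about .118, .076 or .059 for two, three or four visits, the last two under sphericity.

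The conditional part is power for the pilot effect at alpha .05, which runs from about .60 (pre-post partial) through .82 and .93 (three- and four-visit partial) to .996 (already on the plan's scale). At three or four visits power passes .80, but detectable values of .076 and .059 against .08 are not the gap that .03 suggests. The plan's wide margin, and the adequacy claim drawn from it, are supported only if both figures share the plan's undefined scale. The point concerns Cohort 1 at 75 completers and says nothing about the size or arms of Cohort 2.

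**What to change.** In 15.2:
- Restate the Cohort 1 sensitivity as partial eta-squared for group x time, for the number of visits the test will use: three arms, 75 completers, alpha .05, about .12 (two visits), .076 (three) or .059 (four), with sphericity stated for the last two. At two visits add .18 for alpha .005 and .22 for alpha .001. Do not list a correlation beside these values, because partial eta-squared at a given power does not depend on it.
- Say what kind of eta-squared the pilot .08 is, with its visits and arms, and convert it to the same scale.
- Give the power for it on that scale. If it proves to be a pre-post partial value tested pre-post, that is about .60, and should be worded as conditional until the pilot's scale is confirmed.
- Keep the statements about the margin over the pilot and the adequacy of power only if they hold on the common scale.
- Refer to 75 completers, since 90 are to be enrolled.

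The cost is wording only. The stated sensitivities become less favourable; no extra participants or procedures are needed.
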